6.6 Dose Modification

IMP/IP dose modification is not permitted during the study.

6.7 Treatment after the End of the Study

Subjects will return to their normal standard of care upon completion of the study.

7.0 DISCONTINUATION OF STUDY TREATMENT AND SUBJECT DISCONTINUATION/WITHDRAWAL

7.1 Discontinuation of Study Treatment

If an AE occurs during the administration of study treatment, discontinuation of the infusion may occur if the Investigator believes that it is in best interest of the subject. The subject will then be withdrawn from the study.

If a subject who does not meet the enrollment criteria is inadvertently administered study treatment, that subject may be discontinued from the study and the Sponsor or Sponsor designee must be contacted. An exception may be granted in rare circumstances for which there is a compelling reason to allow the subject to continue. In these rare cases, the Investigator must obtain documented approval from the Sponsor or Sponsor designee to allow the subject to continue in the study.

Subjects who discontinue study treatment will not be replaced.

See the Schedule of Activities ([Section 1.3](#)) for the data to be collected at the time of treatment discontinuation and follow-up and for any further evaluations that need to be completed.

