CADSS = Clinician-Administered Dissociative States Scale; CGI-I = Clinical Global Impression - Improvement; CGI-S = Clinical Global Impression - Severity; C-SSRS = Columbia Suicide Severity Rating Scale; CRF = case report form; DBP = diastolic blood pressure; 5D-ASC = 5-Dimensional Altered States of Consciousness Rating Scale; ECG = electrocardiogram; EQ-5D-3L = European Quality - 5 Dimensions - 3 Levels; EoI = End of Infusion; GAD-7 = Generalized Anxiety Disorder 7-Item Scale; HAM-D = Hamilton Depression Rating Scale; HIV = human immunodeficiency virus; MADRS = Montgomery Åsberg Depression Rating Scale; MGH-ATRQ = Massachusetts General Hospital Antidepressant Response Questionnaire; MINI = Mini-International Neuropsychiatric Interview; MOAA/S = Modified Observer's Assessment of Alertness/Sedation; OCBP = of childbearing potential; PK = pharmacokinetic; QIDS-SR-14 = Quick Inventory of Depressive Symptomatology – 14 Items; QIDS-SR-16 = Quick Inventory of Depressive Symptomatology – 16 Items; SBP = systolic blood pressure.

- a. Subjects who discontinue the study early will complete Visit 4 assessments and procedures as early termination procedures.
- b. All post-dose timepoints are relative to the start of infusion except for the 40-minute (EoI) timepoint. EoI procedures should occur 40 minutes after the start of infusion or at the end of infusion if the infusion continues beyond 40 minutes.
- c. Where activities at a given timepoint coincide, consideration should be given to ensure that the following order of activities is maintained: Efficacy rating scales (where more than one efficacy scale is assessed at a timepoint, the order of assessments should be MADRS, CGI-I and CGI-S, QIDS-SR-14/16, HAM-D, GAD-7 and EQ5D-3L); 12-lead ECGs; vital signs and pulse oximetry; safety rating scales (order: MOAA/S, CADSS and BPRS+); AE review, concomitant medication review, physical exam, and clinical laboratory assessment (including urine pregnancy test and drug/alcohol screen).
- d. Assessments and procedures should be started as close as possible after the EoI.
- e. Check eligibility.
- f. Assess clinical hematology and chemistry tests (non-fasting blood samples will be requested, but both fasting and non-fasting samples are acceptable).
- g. To be collected prior to clinical laboratory assessments. An ECG will be performed after 5 minutes in a supine position, if possible.

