4.0 STUDY DESIGN

4.1 Overall Design

This is a double-blind, randomized, placebo-controlled, multicenter study comprised of 3 phases: screening (up to 2 weeks [Day -15 to Day -2]), In-Clinic Treatment (Day -1 to Day 2; including double-blind treatment [Day 1]), and post-treatment follow-up (7 and 14 days after infusion, on Days 8 and 15, respectively). The study consists of 3 arms: placebo, PCN-101 Solution for Injection 30 mg, and PCN-101 Solution for Injection 60 mg. A total of 93 adult subjects with TRD will be randomly allocated in equal cohorts of 31 subjects/arm to the 3 arms of the study in a blinded manner. Randomization will be stratified by region (US, EU).

Subjects will be randomized within 14 days of screening (Visit 1). Subjects will be admitted to the clinic the evening prior to study treatment administration (Day -1, Visit 2) and undergo baseline testing to ensure continued study eligibility. Study treatments will be infused IV over 40 minutes the next morning (Day 1, Visit 2). Starting immediately prior to dosing, subjects will be monitored closely for safety. Additionally, the subjects' alertness, mood, and other psychological parameters will be assessed by clinician- and patient-completed scales and questionnaires. Subjects will be discharged no earlier than 24 hours postinfusion and after the final in-clinic assessments have been completed (Day 2, Visit 2). Subjects will be asked to return to the clinic approximately 6 days (Day 8, Visit 3) and 13 days (Day 15, Visit 4) after discharge to assess the safety and tolerability of the study treatments and to determine the durability of the antidepressant effect.

During the coronavirus disease 2019 (COVID-19) pandemic, the specific guidance from local public health and other competent authorities regarding the protection of individuals' welfare must be applied. If subjects cannot attend follow up visits in person because of restrictions arising as a consequence of the COVID-19 pandemic, the Investigator must discuss with the Medical Monitor potential mitigation.

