8.0 STUDY ASSESSMENTS AND PROCEDURES

Investigator or his/her qualified designee must have completed the sponsor specified training for each rating scale (where appropriate), before any rating scales are completed, and some additional training certification may be required prior to site activation. To maintain the study blind, the staff member that completes the efficacy scales should not complete any safety scales, except for C-SSRS, or assessment of adverse events for any given subject. Similarly, the staff member that completes the safety scales should not complete any efficacy scales for any given subject. To ensure consistency, the same staff member (where possible) should complete the questionnaires for each subject throughout the study.

All post-dose timepoints in the Schedule of Activities (Section 1.3) are relative to the start of the infusion, except for the 40-minute (end-of-infusion [EoI]) timepoint. EoI procedures should occur 40 minutes after the start of infusion or at the end of infusion if the infusion continues beyond 40 minutes.

EoI procedures include 12-lead ECG, vital signs, pulse oximetry, CADSS, and BPRS+. MOAA/S continues on 20 minute intervals from the start-of-infusion and AE review will be continuous from predose to 4 hours postdose.

For the EoI, a time window of \pm 2 minutes after the 40-minute total time is allowed. Assessments and procedures, however, should be started as close as possible after EoI.

From predose on Day 1 to the end of the study, the highest priority procedures will be performed closest to the nominal time. Where activities at a given timepoint coincide, consideration should be given to ensure that the following order of activities is maintained. Deviations are not required when the actual order differs from the following.

- Efficacy rating scales. Where more than one efficacy scale is assessed at a timepoint, the order of assessments should be MADRS, CGI-I and CGI-S, QIDS-SR-14/16, HAM-D, GAD-7 and EQ5D-3L.
- 12-lead ECGs
- Vital signs and pulse oximetry
- Safety rating scales. Where more than one safety scale is assessed at a timepoint, the order of assessments should be MOAA/S, CADSS and BPRS+.
- AE and concomitant medication review.
- Physical examination
- Clinical laboratory assessments (including urine pregnancy test and drug/alcohol screen).

Study procedures and their timing are summarized in the Schedule of Activities in Section 1.3.

Protocol waivers or exemptions are not allowed.

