Immediate safety concerns should be discussed with the Sponsor immediately upon occurrence or awareness to determine if the subject should continue or discontinue study treatment.

Adherence to the study design requirements, including those specified in the Schedule of Activities, is essential and required for study conduct.

All screening evaluations must be completed and reviewed to confirm that potential subjects meet all eligibility criteria. The Investigator will maintain a screening log to record details of all subjects screened and to confirm eligibility or record reasons for screening failure, as applicable.

Procedures conducted as part of the subject's routine clinical management (eg, blood count) and obtained before signing of the ICF may be utilized for screening or baseline purposes provided the procedures met the protocol-specified criteria and were performed within the time frame defined in the Schedule of Activities.

Screening and/or baseline procedures will include:

- Obtain informed consent.
- Confirm that the subject meets all eligibility criteria.
- Record the subject's demographic information.
- Perform a physical exam (include recording of the subject's height, weight, and BMI).
- Record the subject's medical history.
- Conduct screening tests for HIV, hepatitis B, and hepatitis C.
- Record the subject's prior and concomitant medications.
- For subjects OCBP, perform a serum pregnancy test at screening and a urine pregnancy test at baseline.
- Conduct laboratory assessments.
- Conduct a 12-lead ECG, vital signs, pulse oximetry.
- Conduct a urine alcohol and drug screen (at a minimum will include ketamine, opiates, cocaine, barbiturates, and/or amphetamine/methamphetamine).
- Review AEs.
- Perform a MINI version 7.0.2 to assess the 17 most common psychiatric disorders in DSM-III-R, DSM-IV, DSM-V, and ICD-10. The MINI is designed as a brief structured diagnostic interview to meet the need for a short but accurate structured psychiatric

interview for multicenter clinical trials and epidemiology studies and to be used as a first step in outcome tracking in non-research clinical settings. The MINI is a structured interview in which patients are asked to answer questions “Yes” or “No” (eg, “Were you ever depressed or down, or felt sad, empty or hopeless most of the day, nearly every day, for two weeks?”). The MINI is designed to map onto diagnoses defined by the DSM-5 (37).

- Perform an MGH-ATRQ, HAM-D, MADRS, and C-SSRS.

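### Protocol 7.1 withdraws a subject whose infusion is stopped for an AE, and no rule says that the remaining Day 1 CADSS, BPRS+ and MOAA/S readings are still taken

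*Protocol*

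**What the plan says.** Protocol 7.1 lets the infusion be stopped when an AE occurs during it, "if the Investigator believes that it is in best interest of the subject. The subject will then be withdrawn from the study". Subjects who stop treatment are not replaced. The section then refers to the Schedule of Activities (1.3) "for the data to be collected at the time of treatment discontinuation and follow-up and for any further evaluations that need to be completed".

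In 1.3 the only instruction about leaving early is footnote a, attached to the Visit 4 (Day 15) column: "Subjects who discontinue the study early will complete Visit 4 assessments and procedures as early termination procedures". Sections 8.2.6 to 8.2.8 place every post-dose CADSS and BPRS+ within 4 hours of the start of infusion and every MOAA/S within 6 hours. None of the three is scheduled at Visit 4.

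Other text favours continued collection:
- Protocol 4.1: "Subjects will be discharged no earlier than 24 hours postinfusion and after the final in-clinic assessments have been completed".
- Protocol 8.0: "Adherence to the study design requirements, including those specified in the Schedule of Activities, is essential and required for study conduct", and "Protocol waivers or exemptions are not allowed".
- Protocol 8.0 on timing, with the end-of-infusion (EoI) timepoint as the one exception: "All post-dose timepoints in the Schedule of Activities (Section 1.3) are relative to the start of the infusion".
- Appendix 4 asks for supplemental evaluations after an AE where medically needed. It names no scale.

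SAP VIII.I summarises the three scales descriptively, by arm and scheduled timepoint, and lists the scores by subject.

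**The concern.** The three scales are named variables for the safety objective. Sedation, psychotic effects and dissociation are among the effects on which 30 mg and 60 mg compared favourably with 100 mg and 150 mg (Protocol 4.3). The by-timepoint summary in SAP VIII.I is the only by-arm table of these scales.

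A subject whose infusion is stopped for an AE is informative for that table. If 7.1 and footnote a are taken as the specific rule for this subject, the next required procedures are those of Visit 4, and the remaining Day 1 readings are not taken. Readings would then be missing for a reason linked to tolerability. With about 20 centers, practice could also differ between sites.

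**Working it through.** The plan gives no figure on this point. The only design number used here is the 31 subjects per arm in Protocol 9.2. That sample size reproduces: with a difference of 8, SD 11 and two-sided alpha 0.05, the noncentral t gives power 0.804 at 31 per arm. Nothing below depends on it beyond the denominator.

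**Step 1. Does any rule reach a withdrawn subject?**

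| Text | Direction | Speaks of a withdrawn subject? |
|---|---|---|
| 7.1, stop for an AE | withdrawal, then refers to 1.3 | yes |
| 1.3 footnote a | Visit 4 procedures | yes, early discontinuation |
| 4.1, stay of at least 24 hours | favours collection | no |
| 8.0, adherence and no waivers | favours collection | no |
| 8.0, timing from start of infusion | favours collection | no |
| Appendix 4, AE follow-up | favours evaluation | scales not named |

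The two texts that address this subject do not ask for the scales. The texts that favour the scales do not address this subject.

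**Step 2. Readings at stake for one subject.** Scheduled post-dose times, in minutes from the start of infusion:
- CADSS (8.2.7): 40 (EoI), 120, 240, which is 3 readings.
- BPRS+ (8.2.8): 40 (EoI), 120, 240, which is 3 readings.
- MOAA/S (8.2.6): 20, 40, 60, 80, 100, 120, 240, 360, which is 8 readings.

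Stop before minute 20: 3 + 3 + 8 = 14 remain. Stop between minutes 20 and 40: 3 + 3 + 7 = 13 remain. The last is at 360 minutes (6 hours), well inside the 24-hour stay.

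**Step 3. Share of an arm.** If k of 31 subjects have no later readings, each affected timepoint loses k/31 of that arm's readings:
- k = 1: 1/31 = 3.2%
- k = 2: 2/31 = 6.5%
- k = 3: 3/31 = 9.7%

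**Step 4. How many subjects?** The documents give no rate of stopping for an AE. The rates p below are assumptions. The expected number is 31p per arm and 62p over the two active arms.

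| Assumed p | 31p | 62p |
|---|---|---|
| 1% | 0.31 | 0.62 |
| 2% | 0.62 | 1.24 |
| 5% | 1.55 | 3.10 |

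**The case against.** The case against has four parts.

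**Footnote a cancels nothing.** It sits on the Visit 4 column and makes that visit double as the exit visit. It does not say that only those procedures are done. Section 7.1 refers to the whole Schedule, which contains the Day 1 scales, and its wording fixes no moment of withdrawal. This stands. A reader might infer that the protocol orders the Day 1 scales to be dropped; the documents do not say so, and a site could complete them first.

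**The plan expects data from partly dosed subjects.** An incomplete infusion is an intercurrent event under a treatment-policy strategy, the FAS admits subjects with any amount of treatment, and one sensitivity analysis is restricted to treatment-compliant subjects. This shows intent, but the treatment-policy text concerns efficacy and uses values that are observed. It does not order collection.

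**The harm stays visible.** The AE enters the TEAE tables, including those for severe events and for discontinuation of treatment. Disposition gives the reason for leaving, a lost reading shows as a smaller n, and any score taken is listed. This stands, and it limits the consequence. What could be missing is the scored severity and time course.

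**The EoI timing is already settled.** A reader might infer that EoI is undefined when an infusion stops early. Protocol 8.0 answers this: "EoI procedures should occur 40 minutes after the start of infusion or at the end of infusion if the infusion continues beyond 40 minutes". An early stop falls under the 40-minute branch, so there is no gap to repair.

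**Conclusion.** The point holds as a possible loss of data under an unclear rule. For one subject it covers up to 14 readings (13 for a stop between minutes 20 and 40), or 3.2% of an arm's readings per affected timepoint. It rests on a site treating 7.1 and footnote a as overriding the general rules, which the text permits but does not require. The exposed output is one descriptive, untested summary. The safety set, the AE and discontinuation tables and the infusion-duration summary are unaffected.

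Two further inferences are not supported:
- **A stopping rate.** A reader might take Protocol 4.3 to mean that stops will be rare. It compares doses and reports no infusion stops, so it supports no rate. The 1% to 5% above is an assumption.
- **A bias of known size and direction.** If the stop was for dissociation, psychotic symptoms or sedation, missing readings would tend to make that arm look milder. If it was for hypertension or nausea, no direction follows. Rescue medication is allowed (6.5), so stopping is not the only response. No size can be given.

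This is a cheap improvement to the wording, not a flaw that threatens the trial's conclusions.

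**What to change.** In Protocol 7.1, replace the withdrawal sentence, and align footnote a of 1.3 with it: a subject whose infusion is stopped for an AE discontinues study treatment but remains in the study for all remaining scheduled in-clinic assessments through 24 hours, unless consent is withdrawn, and then has the early-termination (Visit 4) procedures.

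The cost is one sentence in two places. The assessments are already scheduled and fall within the planned stay. The downside is a small burden on a subject who has just had an AE. The same sentence would also retain the 24-hour MADRS, which the treatment-policy strategy for an incomplete infusion uses when it is observed. No change is needed to the EoI wording or to SAP VIII.I.

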3.0 OBJECTIVES AND ESTIMANDS

The study objectives and estimands are presented in [Table 1](#).

Table 1 Study Objectives and Estimands

Objectives	Estimands
Primary	
To determine the efficacy of 2 doses (30 mg and 60 mg) of IV PCN-101 compared with placebo in improving depressive symptoms in subjects with TRD as assessed by change from baseline to 24 hours after the start of the infusion of PCN-101 in the Montgomery Åsberg Depression Rating Scale (MADRS) total score.
 
The primary estimand is defined as follows
 
 Population: Subjects with TRD in the full analysis set (FAS) and analyzed according to their randomized treatment. The analysis population includes all randomized subjects who receive any amount of study treatment and have at least 1 postbaseline assessment available. Variable: Change in total MADRS score from baseline at 24 hours after the start of infusion. Intercurrent event (ICE): Incidents where a subject does not receive the full treatment infusion will be considered an intercurrent event. The intercurrent event will however be handled using a treatment policy where all observed values will be used regardless of occurrence of an intercurrent event. No imputation is performed in the primary efficacy analysis. Population-level summary: Difference in mean change from baseline between each PCN-101 group versus placebo 
Additional methodology will be specified in the Statistical Analysis Plan (SAP) for sensitivity and supplementary analyses for assessing the robustness of results. These sensitivity or supplementary analyses will explore different methods for handling intercurrent events and different assumptions for missing data.

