8.1.1 Montgomery Åsberg Depression Rating Scale

The 10-item MADRS will be administered by the study staff to measure the overall severity of depressive symptoms. The MADRS total score will be assessed at screening and baseline (Day 1 predose).

- The primary efficacy endpoint of improvement in the MADRS total score will be evaluated prior to discharge on Day 2 of Visit 2, 24 hours after the start of the infusion of study treatment.
- The MADRS total score will also be assessed at 2 hours, 4 hours, 7 days (on Day 8), and 14 days (on Day 15) after the start of the infusion of PCN-101 to evaluate the secondary efficacy endpoints of (1) response (defined as $\geq 50\%$ improvement in the MADRS total score from predose) and (2) remission (defined as MADRS total score ≤ 10) in the improvement of depressive symptoms in the subjects.
- While the MADRS is typically used with a 7-day recall period, versions of the MADRS including 2-hour and 24-hour recall periods will be used in this study. (For the 2 hour and 4 hour periods, the sleep and appetite items will not be assessed; predose scores for these items obtained on the same day will be carried forward).

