Table 2 Description of Analysis Sets

Analysis set	Description
Screened Analysis Set	All subjects who signed the informed consent form.
Full Analysis Set (FAS)	
The FAS will consist of all randomized subjects who receive any amount of study treatment and have at least 1 postbaseline assessment available. This population will serve as the basis for efficacy analysis.
 
Subjects will be analyzed according to their randomized treatment.

Safety Analysis Set (SAS)	
The SAS will consist of all randomized subjects who receive any amount of study treatment.
 
This analysis set will be used for all summaries of subject disposition, demographic and baseline data, and safety information including AE incidence.
 
Subjects will be analyzed according to the treatment they actually received.

H. Subgroups of Analysis Populations

Data from subgroups of subjects in the defined analysis populations will be analyzed as specified below. These analyses will comprise descriptive summaries; the goal will be to identify signals of additional effects that analyses of data from the defined populations do not take into account. Such analyses will be considered exploratory and other subgroups may be considered. They may not be sufficient for drawing conclusions; hence, these analyses will not involve hypothesis testing.

- Age Group (18-44, 45-65 years))
- Sex (Male, Female)
- Region (United States or Europe)
- Duration of depression (<5 years, 5-10 years, > 10 years)
- Duration of current episode of depression (weeks)
- Number of previous treatment failures in the current episode (<3, >=3)
- Baseline MADRS Score (<35, ≥35)
- Baseline medication
 - o Selective Serotonin reuptake inhibitor (SSRI)

- o Serotonin and norepinephrine reuptake inhibitor (SNRI)
- o Antidepressant with adjunctive medications

I. Data Display Characteristics

Data displays produced for this study will include three types—summary tables, data listings, and figures. Unless stated otherwise, data listings will be produced for all recorded data. Summary tables will be produced as specified in the following sections. Additional data listings will be produced for outcome measures that involve extensive procedures to derive the analyzed outcomes. Figures will be produced when specified in sections to follow.

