Medical history will be coded using Medical Dictionary for Regulatory Activities (MedDRA) version 23.0 or higher. System Organ Class (SOC) and Preferred Term (PT) will be summarized by number and percentage of subjects having at least one occurrence of the event for the FAS only. All Medical history information be listed by subject.

E. Population Inclusions

A hierarchical table of the populations in which Screened Analysis Set subjects were included will summarize the relationship of the analysis populations. Given population definitions, the Screen Analysis Set will be treated as the parent analysis set. The numbers and percentages of Screened Analysis Set included in the FAS, SAS and PPAS will be presented for each treatment group. The numbers and percentages of FAS subjects included in the SAS and PPAS population will be displayed for each treatment group. This table will be produced for subjects in both US and Europe regions, and as an overall.

VII. Efficacy Analyses

The analysis of the efficacy data obtained from the subjects in this clinical study will be performed on the FAS primarily.

All efficacy analyses will be performed based on a subject's randomized treatment group.

A. Primary Estimand

The primary estimand is defined as follows

- **Population:** Subjects in the FAS and analyzed according to their randomized treatment. The analysis population includes all randomized subjects who receive any amount of study treatment and have at least 1 postbaseline assessment available.
- **Variable:** Change in total MADRS score from baseline at 24 hours after the start of infusion.
- **Intercurrent event:** Incidents where a subject does not receive the full treatment infusion will be considered an intercurrent event. The intercurrent event will however be handled using a treatment policy where all observed values will be used regardless of occurrence of an intercurrent event. No imputation is performed in the primary efficacy analysis.
- **Population-level summary:** Difference in mean change from baseline between each PCN-101 group versus placebo

Additional methodology will be specified for sensitivity and supplementary analyses for assessing the robustness of results. These sensitivity or supplementary analyses will explore different methods for handling intercurrent events and different assumptions for missing data.

B. Primary Efficacy Endpoints

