Within a single analysis timepoint per patient, if $\geq 25\%$ of items used to calculate a total score for a given scale are missing, the total scale score for that patient and timepoint will be considered missing.

If $<25\%$ of items are missing, the total score will be calculated (prorated) as the arithmetic mean of non-missing items multiplied by the total expected number of items and rounded up to the nearest integer.

Additionally, separate sensitivity analyses will be performed with missing MADRS data imputed with a multiple imputation method. The multiple imputation (MI) method assumes a missing-at-random (MAR) data missing pattern. Imputation will be performed using the Fully Conditional Specifications parametric regression model. A total of 50 imputations will be generated using PROC MI. For each of the 50 datasets, missing MADRS total score will be imputed using the regression model, as implemented in the PROC MI with the following variables considered (as given on the VAR statement): Treatment, Region, Baseline MADRS and each subsequent post-baseline MADRS score. Response status (Yes, No) and revised change from baseline values will be derived in each MI dataset based on the newly imputed data. The seed to be used in this MI model is 60773.

Example SAS code for PROC MI is as follows:

```
PROC MI DATA=MI NIMPUTE=50 SEED=&SEED. OUT=MI1 ROUND=1 MINIMUM=0;
  CLASS TRTP REGION1;
  VAR TRTP REGION1 ATPTN20 ATPTN40 ATPTN50 ATPTN70 ATPTN80
  ATPTN90;
  FCS REG (ATPTN20 = TRTP REGION1);
```

```
FCS REG (ATPTN40 = TRTP REGION1 ATPTN20) ;
FCS REG (ATPTN50 = TRTP REGION1 ATPTN20 ATPTN40 ) ;
FCS REG (ATPTN70 = TRTP REGION1 ATPTN20 ATPTN40 ATPTN50) ;
FCS REG (ATPTN80 = TRTP REGION1 ATPTN20 ATPTN40 ATPTN50
ATPTN70 ) ;
FCS REG (ATPTN90 = TRTP REGION1 ATPTN20 ATPTN40 ATPTN50
ATPTN70 ATPTN80) ;
RUN;
```

Note: TRTP = randomized treatment group, REGION1 = region (US/Europe). Note: Each of the ATPTNxx variables represent the MADRS score at each analysis timepoint (Pre-dose, 2 hours, 4 hours, 24 hours, Day 8 and Day 15).

The imputation models may be modified based on the actual data if there is an issue in model convergence. If the missingness at the MADRS 24 hour timepoint is >5%, additional analyses exploring missing-not-at-random (MNAR) assumptions will be performed.

F. Primary Efficacy Outcome Analysis

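### Protocol 7.1 withdraws subjects whose infusion is stopped for an adverse event, although the efficacy estimands handle that event by treatment policy and need their later MADRS ratings

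*Protocol*

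**What the plan says.** **The estimand.** SAP VII.A states: "Incidents where a subject does not receive the full treatment infusion will be considered an intercurrent event". Protocol 3.0, Table 1 uses the same definition and handles the event by treatment policy, so that "all observed values will be used regardless of occurrence of an intercurrent event". The primary variable is the MADRS change at 24 hours. Protocol Table 1 and SAP VII.C apply the same strategy to the secondary efficacy estimands, which include MADRS on Days 8 and 15.

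**The withdrawal rule.** Protocol 7.1 lets the investigator stop the infusion for an adverse event and continues: "The subject will then be withdrawn from the study". These subjects are not replaced. For data at discontinuation and at follow-up, 7.1 refers to the Schedule of Activities. The only rule there written for early leavers is footnote a: "Subjects who discontinue the study early will complete Visit 4 assessments and procedures as early termination procedures".

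**The general rules.** Protocol 4.1: "Subjects will be discharged no earlier than 24 hours postinfusion and after the final in-clinic assessments have been completed". Protocol 8.1.1 says the primary MADRS "will be evaluated prior to discharge on Day 2 of Visit 2, 24 hours after the start of the infusion". Neither mentions subjects withdrawn under 7.1.

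**The analysis.** The full analysis set (FAS) in SAP V.G, Table 2 takes "all randomized subjects who receive any amount of study treatment and have at least 1 postbaseline assessment available". The primary analysis is an MMRM on observed cases under missing at random (MAR), without imputation (SAP VII.F). Multiple imputation under MAR, a completer analysis and a treatment-compliant analysis are sensitivity analyses (SAP VII.E and VII.G). SAP VII.E adds: "If the missingness at the MADRS 24 hour timepoint is >5%, additional analyses exploring missing-not-at-random (MNAR) assumptions will be performed".

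**The concern.** A treatment-policy strategy asks what happens to subjects whether or not the infusion was completed. It works only if they are still rated after the infusion stops. For stops due to an adverse event, Protocol 7.1 instead makes withdrawal from the study mandatory. So the event after which the estimand most needs data is one after which the protocol tells the site to take the subject out.

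Two things are at stake. The 24-hour MADRS, the primary value, may not be taken if a site reads 7.1 with footnote a and carries out early-termination procedures on Day 1. The Day 8 and Day 15 ratings are no longer scheduled at all for a withdrawn subject. In both cases the value is missing because of poor tolerability, and the model fills the gap under MAR. If stopped subjects fare differently from that prediction, the estimated difference departs from what the treatment-policy wording promises.

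**Working it through.** **1. The plan's own figure.** Protocol 9.2 gives 31 per arm, a difference of 8, SD 11 and two-sided alpha 0.05. A two-sample t-test (noncentral t) gives 80.4% power, matching the stated 80%. Losing 1, 2 or 3 subjects from one active arm gives 79.8%, 79.1% or 78.3%. Power is not the issue.

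**2. What happens to an AE-stopped subject.**

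- *FAS membership.* The definition asks for any postbaseline assessment, not a MADRS. MOAA/S is recorded every 20 minutes for the first 2 hours (Protocol 8.2.6) and SpO2 continuously to 4 hours (8.2.2). A stopped subject would nearly always be in the FAS.
- *24-hour MADRS taken.* It enters the MMRM, and the primary estimand is served.
- *Only 2-hour or 4-hour MADRS available.* The 24-hour value is handled under MAR, given those scores and the rest of the arm.
- *In the FAS with no postbaseline MADRS.* The subject contributes nothing to the MMRM.
- *Days 8 and 15.* There are no scheduled ratings after withdrawal, only one set of Visit 4 procedures as early termination.

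**3. Size of the possible bias at 24 hours.** The documents give no stop rate and no outcome for stopped subjects, so the following are assumptions: 0 to 3 stops of 31 in one active arm, none on placebo, no 24-hour MADRS for any of them, and a true 24-hour change 4 to 8 points away from the MAR prediction.

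Shift in the estimated difference = (stops / 31) × gap.

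| Stops | Gap 4 | Gap 8 |
|---|---|---|
| 0 | 0 | 0 |
| 1 | 0.13 | 0.26 |
| 2 | 0.26 | 0.52 |
| 3 | 0.39 | 0.77 |

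The standard error of the difference is 11 × √(2/31) = 2.79, so the largest entry is 0.77 / 2.79 = 0.28 SE. If stopped active subjects do worse than predicted, the drug effect is overstated by this amount. If they do better, it is understated by the same amount. Stops on placebo reverse these signs.

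**4. How far the early scores help.** Assume equal SDs and a common between-visit correlation r. The combined regression weight of the 2-hour and 4-hour scores is then 2r/(1 + r). Suppose an 8-point deficit is already fully present at 2 and 4 hours:

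- r = 0.5: weight 0.667, residual gap 8 × 0.333 = 2.67, shift 3/31 × 2.67 = 0.26.
- r = 0.8: weight 0.889, residual gap 8 × 0.111 = 0.89, shift 3/31 × 0.89 = 0.09.

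If the deficit does not show early, the shift stays at 0.77.

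**5. What the sensitivity analyses cover.** Multiple imputation shares the MAR assumption. The completer analysis leaves out withdrawn subjects. The compliant analysis leaves them out if the infusion ran under 35 minutes (SAP VIII.A). The missing-not-at-random analyses depend on more than 5% missing at 24 hours. One missing subject is 1/93 = 1.1% of the trial or 1/31 = 3.2% of an arm, so a single case would not start them.

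**The case against.** The strongest reply is that the 24-hour value will be collected anyway. Subjects stay in clinic for at least 24 hours and are rated before discharge, with no exception stated for stopped infusions. Section 7.1 itself refers to the Schedule for data at follow-up as well as at discontinuation, and the Schedule contains the 24-hour MADRS. Footnote a adds procedures and cancels none. Much of this stands: collection at 24 hours is likely, and a reader who inferred that the plan discards the primary value would go beyond the text. It does not settle the matter, because none of these rules says that it survives withdrawal, and they do nothing for Days 8 and 15.

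A reader might also infer that stopped subjects drop out of the FAS and so out of the estimand. The documents do not support that, since almost any safety assessment after the start of infusion qualifies.

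The third reply is that the numbers are assumed. That also stands. An 8-point gap equals the whole planned effect, and nothing in the documents says that stopped subjects would do worse rather than better. Few stops are plausible: Protocol 2.3 and 4.3 report acceptable safety for single infusions up to 150 mg, the doses here are 30 and 60 mg, and 6.5 allows rescue medication.

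**Conclusion.** The point holds as a minor one. A stated rule in Protocol 7.1 works against the treatment-policy strategy of the primary and secondary efficacy estimands. It puts the 24-hour MADRS at some risk and ends the scheduled Day 8 and Day 15 ratings for subjects stopped for an adverse event. It covers only those stops, not every incomplete infusion.

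At 24 hours the possible bias is about 0 to 0.77 points in either direction, at most 0.28 SE, under the assumed 0 to 3 stops of 31 in one arm, all without a 24-hour value, and an assumed gap of 4 to 8 points. Early scores may shrink it to 0.26 or 0.09. Zero stops, and so zero bias, is credible. The documents do not support calling the primary result unreliable on this ground, nor claiming that any bias would favour the drug.

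**What to change.** Amend Protocol 7.1 and Schedule footnote a so that stopping the infusion ends study treatment only. Unless consent is withdrawn, the subject completes the already scheduled 24-hour, Day 8 and Day 15 MADRS, and those values enter the analysis. The investigator's discretion to stop the infusion is unchanged, and no new procedure is added.

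The cost is a short amendment that needs ethics committee and, where applicable, regulatory approval (Protocol Appendix 2). It cannot reach subjects already dosed.

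Optionally, add one sensitivity analysis to the SAP with placebo-based imputation for any subject stopped for an adverse event who has no 24-hour MADRS. SAP I.B allows changes until database lock, so this can still cover subjects already dosed. It costs one extra analysis and is not needed if there are no such subjects.
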